8.3.9 Missing, Unused & Spurious Data

Every effort must be taken by the Principal Investigators and designated site personnel to ensure that all data required on every CRF is obtained and recorded. Missing data is documented as “ND” (“Not Determined”) on the CRF.

Additionally, BVT minimize the incidence of missing data through appropriate management of the clinical investigation, proper screening of study participants as well as thorough training of investigators, monitors and study coordinators.

The analysis of the endpoints will be performed with and without missing data using the Last Observation Carried Forward (LOCF) as main missing data imputation technique.

If appropriate, a set of additional missing data imputation methods will be employed to determine the impact of missing or incomplete data on the study conclusions.

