6.4.2 Primary Safety Endpoints

- Acute device safety, defined as the absence of procedural complications (hemopericardium, hemothorax, pneumothorax, blood transfusion, resuscitation, emergency post-procedural intervention, transfer to an intensive care unit, and death) at discharge and 7 days post procedure.
- Overall device and procedure related anticipated adverse events compared to historical safety data from CV placement procedures.

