7.3 Subject Enrollment

A subject will be considered “enrolled” in the study when they have completed informed consent, are qualified per all study screening requirements and component of the investigational study device is inserted into the subject.

Once a subject has been exposed to the study device, even if the Investigator is unable to complete the Surfacer treatment, the study subject will be considered part of the intent-to-treat population and will be followed up to 7 days post-procedure, or until any adverse events are resolved.

See Section 8.0 for description of analysis populations and statistical considerations.

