7.6 Subject Withdrawal

Subject study participation is voluntary and subjects may withdraw from the study at any time without penalty or compromise to their medical care. Additionally, a subject may be withdrawn from the study at any time at the discretion of the Principal Investigator, if the Principal Investigator believes that continuation in the study could result in unnecessary risks or jeopardize the subject's health and welfare.

The reason for withdrawal will be documented at the time of study withdrawal. All study data collected up to the point of withdrawal will be included in the data analysis and maintained as part of the study documentation.

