8.3.4 Analysis Populations

Enrolled Population:

Study results will be analyzed and reported for all enrolled patients who sign the informed consent, complete the screening procedures are eligible and enrolled in the study.

Intent-to-treat (ITT) Population:

The ITT safety subject population comprises all enrolled subjects in whom Surfacer System usage was attempted (i.e. the first step in the Instructions for Use of the Surfacer System was performed), regardless of whether or not the procedure was completed with the successful placement of a CVC.

Per Protocol Population:

The per protocol (PP) population will include all enrolled subjects in whom the Surfacer System procedure was completed, with a CVC implanted completely and correctly (i.e. the last step in the Instructions for Use of the Surfacer System was performed).

All primary and additional endpoints will be evaluated in both the intent to treat (ITT) and Per Protocol analysis sets. The intent to treat analysis will be considered primary.

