8.3.5 Primary Endpoint Analysis

Descriptive statistics reported for both primary safety and efficacy endpoints will be summarized using number with the event or characteristic, the number evaluated, frequencies, percentages and two-sided exact 95% confidence intervals, or time to event analysis, as appropriate. Fisher's exact test will be carried out for independent proportions comparison. A

¹ Meinert, C. (1986). Clinical Trials: Design, Conduct, and Analysis. Oxford University Press, New York.

critical two-sided alpha level of 0.05 will be used for all statistical evaluations. The primary endpoint study outcomes will be evaluated in the ITT population.

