9.0 SAFETY

Safety monitoring will be performed by the Principal Investigator during the conduct of this study. An Adverse Events (AE) will be recorded and assessed from the time of enrolment through study completion or early withdrawal. All AEs will be followed by the Principal Investigator until resolution or stabilization.

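### For the acute safety endpoint, LOCF counts a subject who is clean at discharge with unknown Day 7 status as complication-free, and no pre-specified analysis bounds that assumption

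*Combined protocol and SAP*

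**What the plan says.** Section 8.3.9 states that the endpoints will be analysed with and without missing data, "using the Last Observation Carried Forward (LOCF) as main missing data imputation technique". It adds: "If appropriate, a set of additional missing data imputation methods will be employed". No method, trigger or scenario is named for that additional set.

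The acute safety endpoint (Sections 6.4.2 and 8.2.1) is binary. It is the absence of a list of complications that ends with "transfer to an intensive care unit, and death) at discharge and 7 days post procedure". Section 8.3.5 evaluates it in the ITT population, which under Section 8.3.4 "comprises all enrolled subjects in whom Surfacer System usage was attempted". It is to be summarised with "two-sided exact 95% confidence intervals, or time to event analysis, as appropriate". No censoring rule accompanies the time-to-event option.

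On follow-up, Section 7.3 says that a subject exposed to the device "will be followed up to 7 days post-procedure, or until any adverse events are resolved". Section 9.0 says that adverse events "will be recorded and assessed from the time of enrolment through study completion or early withdrawal". Section 7.6 lets the investigator withdraw a subject on the belief that "continuation in the study could result in unnecessary risks". It requires the reason to be documented and keeps data collected up to withdrawal in the analysis. Section 7.5 allows for discharge on the same or the next day.

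**The concern.** The plan does not write out how LOCF applies to this endpoint, but the scoring follows from the rule. A subject with a listed complication by discharge is already a failure, whatever happens later. A subject clean at discharge whose Day 7 status is unknown has only the clean record to carry forward, and so becomes a success. The rule therefore cannot turn a true success into a failure. It can only turn an unseen failure into a success. With early discharge, most of the seven days may be imputed rather than observed.

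The exposure is narrow. Reported adverse events, SAEs and deaths are observed data and are not imputed. What remains is an event the site never learns of, for instance after early withdrawal, when adverse event recording ends. Because withdrawal may follow from perceived risk to the subject, unknown status need not be unrelated to outcome.

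At stake is how certain a primary safety rate appears. LOCF keeps the full denominator of 30 and the interval that goes with it, as though every Day 7 status had been seen. Section 8.2.2 justifies the sample size by interval precision rather than power, so the way unknown subjects enter the interval bears on the study's stated output.

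**Working it through.** **Inputs.** N = 30 planned subjects (Section 6.0), a two-sided exact 95% interval (Section 8.3.5) and ITT as primary (Section 8.3.4). The documents give no missing-data rate, so the number m of subjects clean at discharge with unknown Day 7 status is assumed, over a range of 1 to 5.

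**Formula.** For x successes in n, the Clopper-Pearson limits are: lower = 2.5% quantile of Beta(x, n − x + 1); upper = 97.5% quantile of Beta(x + 1, n − x). When x = n, the lower limit is 0.025^(1/n) and the upper limit is 100%.

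**The plan's own figures.** For 27/30 the formula gives 73.5% to 97.9% (width 0.244), and for 15/30 it gives 31.3% to 68.7% (width 0.374). Both match Section 8.2.2.

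**Three treatments of the m unknown subjects.** With c known complications:
- LOCF counts them as successes: (30 − c)/30.
- Complete case drops them: (30 − c − m)/(30 − m).
- Worst case counts them as failures: (30 − c − m)/30.

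With no known complications (c = 0):

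| m (assumed) | LOCF | Complete case | Worst case |
|---|---|---|---|
| 1 | 30/30 = 100% (88.4 to 100) | 29/29 = 100% (88.1 to 100) | 29/30 = 96.7% (82.8 to 99.9) |
| 2 | 30/30 = 100% (88.4 to 100) | 28/28 = 100% (87.7 to 100) | 28/30 = 93.3% (77.9 to 99.2) |
| 3 | 30/30 = 100% (88.4 to 100) | 27/27 = 100% (87.2 to 100) | 27/30 = 90.0% (73.5 to 97.9) |
| 5 | 30/30 = 100% (88.4 to 100) | 25/25 = 100% (86.3 to 100) | 25/30 = 83.3% (65.3 to 94.4) |

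Each unknown subject lowers the worst-case rate by 1/30 = 3.3 points. At m = 3 the worst-case lower limit is 88.4 − 73.5 = 14.9 points below the LOCF limit. The complete-case limit is only 88.4 − 87.2 = 1.2 points below it. Agreement between the two planned analyses would look like robustness, but it says nothing about the subjects whose status is unknown.

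With one known complication and m = 3, the pattern is the same: LOCF 29/30 = 96.7% (82.8 to 99.9), complete case 26/27 = 96.3% (81.0 to 99.9), worst case 26/30 = 86.7% (69.3 to 96.2).

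**Tipping-point table for m = 3, c = 0, on all 30 subjects.** 0 hidden events: 100% (88.4 to 100). 1 event: 96.7% (82.8 to 99.9). 2 events: 93.3% (77.9 to 99.2). 3 events: 90.0% (73.5 to 97.9). The first row is the LOCF result and the last is the worst case.

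**The case against.** The strongest reply is that this is a short, descriptive study that already has safeguards. Follow-up is about a week, with a 7-day window after Day 7. Treated subjects are to be followed to Day 7, withdrawal reasons are recorded, and investigators follow adverse events to resolution or stabilisation. Section 8.3.9 plans an analysis without imputation and further methods meant to gauge the effect of missing data. Section 8.3.5 reports the number evaluated, from which a reader could work out a worst case. All of this stands, and it makes a large m unlikely to be a routine outcome. It does not supply a bound fixed in advance: the complete-case result is also too favourable if hidden events occur, and the rest is discretionary or left to the reader.

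It can also be said that the endpoint may be read as two reported time points, since the schedule in Section 1.3 assesses complications separately at discharge and Day 7. On that reading the discharge rate is untouched, but the Day 7 rate is affected in the same direction.

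A reader might infer an expected bias by applying the 2 out of 136 complication rate in Table 4 (Section 4.1) to the unknown subjects. The documents do not support that:
- Section 4.4 describes 116 of the 136 as procedures, with repeats in the same patients.
- Section 4.3 reports a pocket hematoma in the 8-patient series, while Table 4 lists complications there as not reported.
- The two counted events are hematomas, which are not on the endpoint list.
- Post-discharge events are not separated.

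A reader might also infer that LOCF must be abandoned and the ITT result given only as a worst-to-best range. That would leave no point estimate, and the gap can be closed without it.

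**Conclusion.** The point holds as a minor one. For this endpoint the stated main rule is one-sided, and nothing pre-specified limits how far it could mislead. With no known events and 30 ITT subjects, the worst-case rate is 3.3 points below LOCF for m = 1, 10.0 points for m = 3 and 16.7 points for m = 5.

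These are bounds conditional on an assumed m. The documents give neither a missing-data rate nor a hidden-event risk, so no expected bias can be quoted. If every Day 7 status is known, the three analyses coincide. If no unknown subject had an event, LOCF is correct. Known deaths and serious events are not hidden by the rule. Section 8.2.2 sets no powered target and the plan has no performance goal, so it would be wrong to infer that a pass or fail conclusion could turn on this.

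**What to change.** Add one paragraph to Section 8.3.9, limited to the acute safety endpoint:

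1. Before any imputation, classify every ITT subject from all known adverse event, SAE and death data, whether or not the Day 7 visit took place.
2. Keep the LOCF and complete-case results, and label LOCF as the best case.
3. Pre-specify a worst-case analysis in which unknown Day 7 status counts as not complication-free, with all ITT subjects in the denominator.
4. Pre-specify a tipping-point table with exact 95% intervals for 0 to m events among the m unknown subjects.
5. Report the number with unknown status and the reasons.

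The cost is a few table rows. No subjects, visits or procedures are added. The drawback is that the reported bound may look clearly less favourable if several subjects are missing, so it must be labelled a bound and not an estimate of the complication rate.

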8.3.10 Interim Analysis

No formal interim analysis will be performed.

8.3.11 Subgroup Analysis

No subgroup analysis will be performed.

9.0 SAFETY

Safety monitoring will be performed by the Principal Investigator during the conduct of this study. An Adverse Events (AE) will be recorded and assessed from the time of enrolment through study completion or early withdrawal. All AEs will be followed by the Principal Investigator until resolution or stabilization.

9.1 Adverse Event Classification

9.1.1 Adverse Event

An AE is any undesirable clinical event experienced by a subject participating in a study.

The intensity of an AE will be classified as one of the following:

Mild: transient, does not interfere with the subject's daily activities and does not require therapeutic measures

Moderate: Interferes with the subject's daily activities and requires simple therapeutic measure

Severe: Intolerable experiences that interrupt the subject's daily activities and requires substantial therapeutic measures including surgical intervention or hospitalization

The relationship of the AE to the investigational device will be categorized as one of the following:

Not related: No clinical evidence supporting a causal relationship

Related: Clinical evidence supports a definite and certain causal relationship

9.1.2 Anticipated Adverse Events

A list of AEs which may be anticipated, resulting from use of the study device, are defined in Instructions for Use (IFU) of the investigational device and in Section 5.5 of this protocol.

9.1.3 Serious Adverse Event/Unanticipated Adverse Device Effect

A Serious Adverse Event (SAE) is an AE that meets one of the following criteria:

- fatal
- life threatening
- results in an unanticipated or prolonged hospitalization
- results in a significant and persistent disability/incapacity
- results in a congenital anomaly or birth defect

An unanticipated adverse device effect (UADE) is any SAE as defined above that is caused by or associated with the device, if that effect, problem, or death was not previously identified in nature, severity, degree of incidence in this protocol.

Additionally, a UADE includes any other unanticipated serious problem associated with the device that relates to the rights, safety, or welfare of subjects.

9.1.4 SAE/UADE Reporting

BVT will be notified of an SAE/UADE the SAE/UADE Report Form. This form must be completed by the Principal Investigator or designee, then faxed or scanned and emailed to BVT. The SAE/UADE Report Form, fax number, and email are provided in the study manual.

Initial notification of the SAE/UADE may occur by telephone, but must always be followed by submitting the SAE Report Form by the close of the next business day.

9.1.5 UADE Regulatory Requirements

If it is determined that an UADE occurred, BVT will report the results of the evaluation to the Independent Data Monitoring Committee (IDMC), the FDA, and Principal Investigators within 10 working days after BVT first receives notice of the event (21 CFR 812.46(b), 812.150(b)(1)). If BVT determines an event or event rate presents an unreasonable risk to subjects, the study or parts of the study presenting that risk will be terminated, as soon as possible. Termination of the

study will occur no later than five (5) working days after BVT makes this determination and no later than fifteen (15) days after BVT or its designee first receives notice of the event.

10.0 STUDY MANAGEMENT

10.1 Data Collection

All study data will be collected on standardized electronic Case Report Forms (eCRFs) provided by BVT.

Electronic CRFs must be signed electronically by the Principal Investigator listed in the Clinical Trial Agreement and Delegation of Authority Log. If for any reason an eCRF is unavailable and/or inaccessible, a paper CRF will be provided by the trial Sponsor to be completed, signed by the Principal Investigator or designee and submitted to BVT. Case Report Form Completion Instructions will be provided by BVT to assist the Principal Investigator(s) and appropriate staff with eCRF completion and data entry processes.

BVT or their designee is responsible for database development, validation, control and management using systems that are compliant with 21 CFR Part 11. Databases shall include input(s) from each eCRF, issuance and resolution of queries, database maintenance, and statistical support.

10.2 Source Documentation

BVT and their representatives, review boards (IRB/IEC), and applicable regulatory authorities will be granted access to a subject's medical records related to this study. Original or certified copies of all relevant clinical findings, observations, and other activities throughout the study must be recorded and maintained.

10.3 Data Confidentiality

To protect subject confidentiality, a unique study identifier will be used on all data collected for study purposes. Any data, imaging media, or other form of study record collected shall be de-identified. Original copies of all data must be kept at the site.

10.4 Record Retention

Study documentation and records shall be retained in accordance BVT's internal procedures or those of authorized designee Per FDA regulation 21 CFR, 812.140, records of each subject's participation in the study must be maintained for a period of two (2) years after trial closure and submission of the final report to the IRB.

At a minimum, a copy of the study documents must be retained by the Site for at least five (5) years following the study completion.

Study documentation will not be destroyed without prior written agreement between BVT and the Principal Investigator.

The Principal Investigator is to allow representatives of BVT to inspect all study-related documentation throughout the duration of the study.

10.5 Study Monitoring

BVT or its designee will conduct periodic site monitoring to ensure that all Principal Investigators are in compliance with the protocol and the investigator's agreement. The monitor will verify source documentation against completed eCRFs and resolve any queries/discrepancies.

10.6 Study Oversight and Compliance

Each study site will be visited periodically to ensure that the study is conducted in full compliance with all applicable regulations and this protocol.

BVT or designee shall maintain regular contact with the study site throughout the investigation by telephone, mail, e-mail, and on-site visits. Periodic monitoring visit shall be conducted to ensure continued protocol compliance, adequate subject enrolment, and accurate data reporting.

Following study closure at the study site, BVT or its designee will make a final study visit, to collect any outstanding documentation, ensure that the Principal Investigator's files are accurate and complete, review record retention requirements with the Principal Investigator, make a final accounting of all study supplies shipped to the Principal Investigator, provide for appropriate disposition of any remaining study supplies, and ensure that all applicable requirements for the study are met.

10.6.1 Study Non-Compliance

If BVT or its designee becomes aware that a Principal Investigator is not complying with all study requirements, BVT will evaluate the non-compliance and if necessary, either secure compliance or take other actions until the non-compliance has been resolved.

If the non-compliance is severe or cannot be resolved, BVT retains the right to remove either the Principal Investigator or a study site from the trial.

10.7 Investigational Device Inventory

An initial shipment of investigational devices will be supplied by BVT to IRB/IEC approved study sites.

Additional investigational devices will be supplied to the study site as needed throughout the conduct of the study.

10.7.1 Investigational Device Accountability

Device accountability will be documented and maintained by the Principal Investigator at the study site, to include all investigational devices received, used, and disposed at the end of the study. Investigational device accountability records shall be maintained with clinical study files and be available for review during monitoring visits.

10.7.2 Investigational Device Storage

Investigational devices for use in this study will be stored in a locked, cool, dry and clean area, with controlled accessibility. Only study staff authorized by the investigation will have access to the investigational device.

10.7.3 Investigational Device Return

BVT will provide directions for investigational device return at either study termination or closure. All unused devices and/or those in opened packages must be returned to BVT. The Principal Investigator must document any unused devices that are returned.

10.8 Protocol Deviations

A protocol deviation occurs when the Principal Investigator or study staff do not conduct the study in accordance with the protocol or other agreed upon study terms without prior approval from BVT. Any deviation will be documented and reported to BVT regardless of severity or rationale for deviation.

10.9 Investigator/Site Training

Investigators and site staff will be trained on the study in total, use of the investigational device, and any specialized procedures required for the study. BVT will provide clinical support to site for any questions or concerns related to the investigational device; however, BVT will not have influence on subject care.

10.10 Study Changes

10.10.1 Change to the Protocol

BVT will initiate and document any changes to the protocol in writing. BVT shall submit such changes to the Principal Investigators and applicable regulatory authorities. Approval of the changes must be received by BVT in writing before the may be implemented at the study sites.

10.10.2 IRB/IEC Approval Withdrawal

Withdrawal of IRB/IEC approval must be submitted to BVT within five (5) business days of the change.

10.11 Study Completion

Each Principal Investigator shall be notified in writing upon termination or conclusion of the study. BVT retains the right to suspend or terminate this study at any time.

10.12 Study Reports

Study progress reports shall be prepared and submitted to regulatory authorities per the applicable regulations, or upon request.

A final clinical study report (CSR) will be compiled and submitted once all data collection and analyses have been completed. CSRs shall include all information required and outlined in this protocol that is available at the time of the report. A copy of the final CSR will be provided to applicable regulatory agencies and participating Principal Investigators. The final CSR will be filed and maintained with study documentation.

